## 1.2. Trial Design

This is a Phase 2a, randomized, open-label, multicenter, parallel-group, interventional study to evaluate the efficacy, pharmacokinetics, safety, and tolerability of treatment with JNJ-3989+PegIFN- $\alpha$ 2a +NA regimen with or without JNJ-6379 in patients with HBeAg positive chronic HBV infection and ALT  $\leq$ 2x ULN who are not currently being treated for their HBV infection (i.e., who had <9 months of prior treatment which ended at least 12 months before screening,

including treatment-naïve patients). After completing this study, participants may have the option to enroll into a long-term follow-up study.

A target of approximately 60 adult participants (including approximately 33 after implementation of Protocol Amendment #6), 18-55 years (inclusive) of age (with a maximum of approximately 10 participants  $>45$  to  $\leq 55$  years of age), with CHB who are HBeAg positive, who are not currently treated for their HBV infection (including treatment-naïve patients), have HBV DNA  $\geq 20,000$  IU/mL and have ALT  $\leq 2x$  ULN at screening will be enrolled in this study. It is targeted to enroll at least 30% participants with HBV DNA  $\geq 10^7$  IU/mL and normal ALT at screening in the study.

The study will be conducted in 4 phases:

[figure not shown]
- A screening phase (4 weeks [if necessary, can be extended to a maximum of 6 weeks decided on a case-by-case basis and in agreement with the sponsor]).
- An induction phase:
  - Prior to Protocol Amendment #5: response-guided treatment (RGT) of 36-60 weeks (inclusive).
  - Note: Participants who already passed the Week 36 visit before Protocol Amendment #5 is in effect, will enter the consolidation phase at the next scheduled visit.
  - As of Protocol Amendment #5: fixed duration of 36 weeks for all participants.
- A consolidation phase (12 weeks).
- A follow-up (FU) phase (48 weeks).

The total duration of individual participation will be between 100 and 126 weeks. Of note, participants enrolled after Protocol Amendment #5 will be between 100 and 102 weeks; and the participants enrolled before Protocol Amendment #5 may have a longer induction phase and a total study duration up to 126 weeks.

To distinguish between participants enrolled prior to or after Protocol Amendment #5 is in effect, the terms Cohort 1 and Cohort 2 will be used. All participants enrolled prior to the Protocol Amendment #5 will comprise Cohort 1. RGT criterion is defined as having HBsAg  $<10$  IU/mL. Protocol Amendment #5 was not implemented due to the USM and no participants will be receiving Protocol Amendment #5 treatment, the participants enrolled after approval of Amendment #6 will comprise Cohort 2.

The schematics of the trial changes per Protocol Amendment #5 are presented in [Figure 1](#) and [Figure 2](#) to show the history of protocol amendment.

**Figure 1: Schematic Overview of Cohort 1 of the Study – Prior to Protocol Amendment #5**

[figure not shown]
- a End of the induction phase is defined by either meeting the study defined RGT criterion (HBsAg <10 IU/mL) or reaching study Week 60, whichever comes first. The RGT criterion will be assessed from Week 36 onwards, and the assessment will always be based on lab results from the previous study visit (4 weeks earlier).
- b If NA treatment completion criteria (HBsAg <10 IU/mL, and HBeAg-negative, and HBV DNA <LLOQ, and ALT <3x ULN) have been met at consolidation Week 12, NA will be stopped at the next scheduled visit (ie, FU Week 2), otherwise NA treatment will continue during the complete follow-up phase.

**Figure 2: Schematic Overview of the Study – Per Protocol Amendment 5**

Cohort 1: Participants enrolled before Protocol Amendment #5 is in effect

Per Amendment #5, participants who did not yet reach the Week 36 visit will have PegIFN- $\alpha$ 2a added to their treatment regimen at Week 36 for 12 weeks.

[figure not shown]
Participants who already passed the Week 36 visit and/or were randomized to the group without PegIFN- $\alpha$ 2a, will have PegIFN- $\alpha$ 2a added to their treatment regimen at the next scheduled visit. After 12 weeks, treatment with NA, PegIFN- $\alpha$ 2a, JNJ-3989 and JNJ-6379 (if applicable) will be stopped.

- a If NA treatment completion criteria (HBsAg <10 IU/mL, and HBeAg-negative, and HBV DNA <LLOQ, and ALT <3x ULN) have been met at consolidation Week 12, NA will be stopped at the next scheduled visit (ie, FU Week 2), otherwise NA treatment will continue during the complete follow-up phase.
- b Depending on the approval date of Amendment #5, the induction phase can be longer than 36 weeks for some of these participants.

### Cohort 2: Participants enrolled under Protocol Amendment #5 is in effect

Per Amendment #5, participants will be randomized in a 1:1 ratio at the start of the induction phase to either receive JNJ-3989 + JNJ-6379 + NA or JNJ-3989 + NA for 36 weeks. At Week 36 all participants will have PegIFN- $\alpha$ 2a added to their treatment regimen for 12 weeks.

[figure not shown]

a If NA treatment completion criteria (HBsAg <10 IU/mL, and HBeAg-negative, and HBV DNA <LLOQ, and ALT <3x ULN) have been met at consolidation Week 12, NA will be stopped at the next scheduled visit (ie, FU Week 2), otherwise NA treatment will continue during the complete follow-up phase.

With the implementation of an urgent safety measure, as described in Protocol Amendment 6, participants previously enrolled had to immediately stop JNJ-6379 treatment, because of the removal of JNJ-6379 as study intervention. They were to continue with JNJ-3989+NA treatment up to the end of the induction phase and then enter the 12-week consolidation phase during which PegIFN- $\alpha$ 2a was added to their treatment regimen.

Because of the urgent removal of JNJ-6379 as study intervention, none of the participants enrolled under Protocol Amendment #5 did receive JNJ-6379.

**Figure 3: Schematic Overview of Cohort 2 of the Study – As of Protocol Amendment 6**

a If NA treatment completion criteria (HBsAg <10 IU/mL, and HBeAg-negative, and HBV DNA <LLOQ, and ALT <3x ULN) have been met at consolidation Week 12, NA will be stopped at the next scheduled visit (ie, FU Week 2), otherwise NA treatment will continue during the complete follow-up phase.

As of Protocol Amendment 6, the study will continue as a single-arm study (JNJ-3989+NA+PegIFN- $\alpha$ 2a), as schematized in [Figure 3](#). All newly enrolled participants will receive JNJ-3989+NA for 36 weeks (induction phase) and will then enter the 12-week consolidation phase during which they will have PegIFN- $\alpha$ 2a added to their treatment regimen.

**Key:** ALT: alanine aminotransferase; C: consolidation; DNA: deoxyribonucleic acid; FU: follow-up; HBeAg: hepatitis B e antigen; HBsAg: hepatitis B surface antigen; HBV: hepatitis B virus; JNJ-3989: JNJ-73763989; JNJ-6379: JNJ-56136379; n: number of participants; LLOQ: lower limit of quantification; NA: nucleos(t)ide analog; PegIFN- $\alpha$ 2a: pegylated interferon alpha-2a; R: randomization; RGT: response-guided treatment; ULN: upper limit of normal; Q4W: once every 4 weeks; qd: once daily; QW: once weekly; W: week; WX: last visit of the induction phase ( $\geq$ W36 and  $\leq$ W60) equivalent to Day 1 of the consolidation phase.

The induction and consolidation phase have been updated as below:

- Before Protocol Amendment #5, enrolled participants will enter an induction phase with triple combination treatment (JNJ-3989 + JNJ-6379 + NA) for a response-guided treatment duration of  $\geq$ 36 weeks to  $\leq$ 60 weeks. End of the induction phase is defined by either meeting the study defined RGT criterion (HBsAg  $<10$  IU/mL) or reaching study Week 60, whichever comes first. The RGT criterion will be assessed from Week 36 onwards at each study visit, and the assessment will always be based on lab results from the previous study visit. Participants will be randomized in a 1:1 ratio to one of the following intervention arms in the 12-week consolidation phase: JNJ-3989+JNJ-6379+NA+PegIFN- $\alpha$ 2a (Cohort 1, Arm 1) or JNJ-3989+JNJ-6379+NA (Cohort 1, Arm 2).

**Note:** Participants enrolled before Protocol Amendment #5 is in effect will switch to the new study design as soon as Protocol Amendment #5 is in effect. The details are in the [Figure 2](#) Cohort 1.

- Per Protocol Amendment #5, participants will be randomized at baseline in a 1:1 ratio to one of the following intervention arms: JNJ-3989+JNJ-6379+NA (Cohort 2, Arm 3) or JNJ-3989+NA (Cohort 2, Arm 4). Upon completion of the 36-week induction phase, all participants will enter the 12-week consolidation phase during which they will have PegIFN- $\alpha$ 2a added to their treatment regimen.

**Note:** With the implementation of an urgent safety measure, as described in Protocol Amendment 6, participants previously enrolled had to immediately switch to the new study design. Participants had to stop JNJ-6379 treatment immediately and continue with JNJ-3989+NA treatment up to the end of the induction phase and will then enter the 12-week consolidation phase during which they will have PegIFN- $\alpha$ 2a added to their treatment regimen.

- As of Protocol Amendment 6, the study will continue as a single-arm study (JNJ-3989+NA+PegIFN- $\alpha$ 2a). All newly enrolled participants will receive JNJ-3989+NA for 36 weeks (induction phase) and will then enter the 12-week consolidation phase during which they will have PegIFN- $\alpha$ 2a added to their treatment regimen.

At the end of the consolidation phase, all participants will enter the FU phase and stop treatment with JNJ-3989+PegIFN- $\alpha$ 2a. If NA treatment completion criteria (HBsAg  $<10$  IU/mL, and HBeAg-negative, and HBV DNA  $<$ LLOQ, and ALT  $<$ 3x upper limit of normal [ULN]) have been met at consolidation Week 12, NA will also be stopped at the next scheduled visit (ie, FU Week 2), otherwise NA treatment will continue during the complete FU phase. Participants will be monitored closely during the 48-week FU phase and should restart NA treatment in accordance with the NA re-treatment criteria.

As of protocol Amendment #6, study intervention consists of:

- 200 mg JNJ-3989 (SC injection Q4W)
- 245 mg tenofovir disoproxil (tablets qd) – **Note:** tenofovir disoproxil may be supplied as fumarate or maleate
- 180 µg PegIFN- $\alpha$ 2a (SC injection, QW)

**Note:** Most participants enrolled before Protocol Amendment #6 was in effect, also received 250 mg JNJ-6379 (tablets qd) as part of their study intervention.

All participants will be considered to have completed the study if they have completed the assessments of the end-of-study (EOS) visit (ie, FU Week 48).

A data review committee (DRC) will be commissioned for this study. In addition, an Independent Flare Expert Panel (IFLEP) will be appointed.

### **1.3. Statistical Hypotheses for Trial Objectives**

As this is an exploratory proof of concept (PoC) study, no formal statistical hypothesis has been formulated.

### **1.4. Sample Size Determination**

According to the initial study design, the plan was to enroll 80 participants in the study to achieve at least 70 participants to be randomized in a 1:1 ratio to one of the 2 intervention arms after completion of the induction phase. Based on the number of participants currently enrolled, participants who already passed the Week 36 visit and/or were randomized to the group without PegIFN- $\alpha$ 2a by the time Protocol Amendment 6 is in effect, will have PegIFN- $\alpha$ 2a added to their treatment regimen at the next scheduled visit and will enter the 12-week consolidation phase. For the purpose of the statistical analyses, all participants enrolled prior to Protocol Amendment #5 will comprise “Cohort 1”. Protocol Amendment #5 was not implemented due to the USM and no participants will be receiving Protocol Amendment #5 treatment. All participants enrolled after approval of Protocol Amendment 6 will comprise “Cohort 2”.

With the introduction of the new study design in Protocol Amendment 6 (single-arm), no formal sample size re-calculation was performed. The targeted total sample size (Cohort 1 and Cohort 2 combined) was set to approximately 60 participants. With a sample size of 33 participants in Cohort 2 and assuming a 10% dropout rate, 30 participants in Cohort 2 would be expected to have data for the primary efficacy endpoint at 24 weeks after stopping all study interventions of the consolidation phase and without restarting NA treatment.

If at least 15 (50%) participants are responders, this sample size will allow to conclude with 90% confidence that the true response rate is at least 0.34, with a confidence interval (CI) width of 0.322 (90% CI: 0.339 - 0.661).

## 1.5. Randomization and Blinding

### Randomization

For participants in Cohort 1, a distinction will be made depending on the timing when the ISA protocol Amendment #6 will be in effect. Protocol Amendment #5 was not implemented due to the USM and no participants will be receiving Protocol Amendment #5 treatment.

- If a participant of Cohort 1 is in between Week 36 and 60 and met the RGT criteria prior to Amendment #5 approval, then he/she will be randomly assigned in a 1:1 ratio to 1 of 2 intervention arms (Arm 1 = JNJ-3989+JNJ-6379+NA+PegIFN- $\alpha$ 2a; or Arm 2 = JNJ-3989+JNJ-6379+NA). The randomization is stratified by screening HBV DNA level ( $\geq 10^7$  IU/mL OR  $<10^7$  IU/mL) and timing of meeting the study defined RGT criterion (at Week 36 OR after Week 36 up to Week 48 OR after Week 48 up to Week 60 OR not met before or at Week 60) for participants in Cohort 1.
- If a participant of Cohort 1 has not yet reached Week 36, or did not meet RGT criteria up to Week 60 prior to Amendment #5 approval, then he/she will not be randomized, but will have PegIFN- $\alpha$ 2a added to his/her treatment regimen at the next scheduled visit. After 12 weeks, treatment with NA, PegIFN- $\alpha$ 2a, JNJ-3989 and JNJ-6379 will be stopped, regardless of the actual duration of induction (which may exceed 36 weeks).

For participants in Cohort 2 as of Protocol Amendment #6, the study will continue as a single-arm study (JNJ-3989+NA+PegIFN- $\alpha$ 2a). All newly enrolled participants will receive JNJ-3989+NA for 36 weeks (induction phase) and will then enter the 12-week consolidation phase during which they will have PegIFN- $\alpha$ 2a added to their treatment regimen.

### Blinding

As this is an open-label study, blinding procedures are not applicable.

## 2. GENERAL ANALYSIS DEFINITIONS

The SAP will use throughout the document the following definitions:

The term “**induction phase**” corresponds to the first treatment phase of the study starting with enrollment into induction phase of flexible duration of 36-60 weeks (inclusive) for Cohort 1 and starting with randomization or enrollment into the induction phase of a fixed duration of 36 weeks for Cohort 2.

The term “**consolidation phase**” corresponds to the second treatment phase of the study starting with the first PegIFN- $\alpha$ 2a intake with a fixed duration of 12 weeks for both cohorts.

- *Study treatment/intervention* refers to: JNJ-3989, JNJ-6379, NA (TeD, or TAF) and PegIFN- $\alpha$ 2a prior to Protocol Amendment #6; JNJ-3989, NA (TeD, or TAF) and PegIFN- $\alpha$ 2a as of Protocol Amendment #6.
- *Study agent* refers to: JNJ-3989, JNJ-6379, and PegIFN- $\alpha$ 2a prior to Protocol Amendment #6; JNJ-3989 and PegIFN- $\alpha$ 2a as of Protocol Amendment #6.

- *Study intervention arm* will be specified with Cohort 1 and Cohort 2 which are distinguished between participants enrolled prior to or after Protocol Amendment #6 as the Protocol Amendment #5 was not implemented due to the USM and no participants will be receiving Protocol Amendment #5 treatment. All participants enrolled prior to the Protocol Amendment #5 will comprise Cohort 1. The participants enrolled after approval of Amendment #6 who will comprise Cohort 2. The Study intervention arm in the SAP will be
  - Cohort 1:
    - JNJ-3989 + JNJ-6379 + NA + PegIFN- $\alpha$ 2a
    - JNJ-3989 + NA + PegIFN- $\alpha$ 2a
  - Cohort 2:
    - JNJ-3989 + NA + PegIFN- $\alpha$ 2a

## 2.1. Analysis Phases and Visit Windows

### 2.1.1. Analysis Phase

The analysis phases are defined in [Table 1](#) below.

**Table 1: Analysis Phases Start and End Dates**

Analysis phase	Start date	End date
Screening	The date of signing the informed consent	1 day before the first study agent intake (excluding PegIFN- $\alpha$ 2a)
Induction phase	Cohort1: Date of first study agent intake (excluding PegIFN- $\alpha$ 2a)	Cohort1: Participants who are randomized: Min{Max[Date of first PegIFN- $\alpha$ 2a intake, Date of randomization] -1 day, cut-off date b }  Participants who are not randomized but receive PegIFN-<math>\alpha</math>2a: Min[Date of first PegIFN- $\alpha$ 2a intake-1 day, cut-off date b ]  Participants who are not randomized and did not receive PegIFN-<math>\alpha</math>2a: Min{Min[JNJ-3989 discontinuation date a , early study withdrawal visit date, max(Week 36 to 60 visit date from induction phase)] + 5 days a , cut-off date b }
	Cohort 2: Date of first study agent intake (excluding PegIFN- $\alpha$ 2a)	Cohort 2: Participants who receive PegIFN-<math>\alpha</math>2a: Min[Date of first PegIFN- $\alpha$ 2a intake – 1 day, cut-off date b ]  Participants who did not receive PegIFN-<math>\alpha</math>2a: Min{Min[JNJ-3989 discontinuation date a , early study withdrawal visit date, Week 36 visit date from induction phase] + 5 days a , cut-off date b }

Analysis phase	Start date	End date
Consolidation phase	Cohort 1: Participants who receive PegIFN- <math>\alpha</math>2a: Date of first PegIFN- $\alpha$ 2a intake  Participants who did not receive PegIFN- <math>\alpha</math>2a: date of any study agent intake after Max[Week 36 to 60 visit date]  Otherwise: Missing	Cohort1: Participants who did not withdraw from the study prior to the Consolidation Week (CW) 12 visit date: Min{Max[last intake date of any study agent (excluding NA), CW c 12], JNJ-3989 discontinuation date a } + 5 days a or cut-off date b , whichever occurs first  Participants who withdrew from the study prior to the Consolidation Week 12 visit date: Min[JNJ-3989 discontinuation date a , early study withdrawal visit date] + 5 days a or cut-off date b , whichever occurs first  Otherwise: Missing
	Cohort 2: Participants receive PegIFN- <math>\alpha</math>2a: Date of first PegIFN- $\alpha$ 2a intake  Participants who did not receive PegIFN- <math>\alpha</math>2a: Date of any study agent intake after Week 36 visit date  Otherwise: Missing	Cohort 2: Participants who did not withdraw from the study prior to the Consolidation Week 12 visit date: Min{Max[last intake date of any study agent (excluding NA), CW12], JNJ-3989 discontinuation date a } + 5 days a or cut-off date b , whichever occurs first  Participants who withdrew from the study prior to the Consolidation Week 12 visit date: Min[JNJ-3989 discontinuation date a , early study withdrawal visit date] + 5 days a or cut-off date b , whichever occurs first  Otherwise: Missing
Follow-up	Participants who did not withdraw informed consent during induction or consolidation phase: Max[End date of induction phase, End date of consolidation phase] +1  Otherwise: Missing	Max[study discontinuation date, study completion date] or cut-off date b , whichever occurs first  Otherwise: Missing

a Addition of 5 days is only applicable for JNJ-3989 discontinuation due to Adverse Events and Concomitant Medications.

b Cut-off dates will be defined to match the prespecified timepoints for DRC safety monitoring, interim analyses and the primary and final analyses, respectively.

c CW = Consolidation Week

## 2.1.2. Relative Day by Study Phase

An analysis relative day (ADY) will be calculated for all assessments at all visits for each participant by study phase.

### 2.1.2.1. Induction Phase Relative Day

Induction start date (Induction Day 1) is defined in the Table 1 Induction phase. All efficacy and safety assessments during the induction phase will be assigned an analysis study day relative to this date.

The study day in the induction treatment phase (ADY) is defined as:

$$\text{Induction ADY} = \text{visit date} - \text{Induction start date} + 1$$

for visits on or after induction Day 1, and

$$\text{Induction ADY} = \text{visit date} - \text{Induction start date}$$

for visits before induction Day 1 (Screening phase).

There is no ‘induction Day 0’.

### 2.1.2.2. Consolidation Relative Day

Consolidation start date (Consolidation Day 1) is defined in the [Table 1](#) Consolidation phase.

All efficacy and safety assessments during the consolidation phase will be assigned an analysis study day relative to this date.

The consolidation study day in the consolidation treatment phase (ADY) is defined as:

$$\text{Consolidation ADY} = \text{visit date} - \text{Consolidation start date} + 1$$

for visits on or after consolidation Day 1. There is no ‘consolidation Day 0’.

### 2.1.2.3. Follow Up Relative Day

Follow Up (FU) start date (FU Day 1) is defined in [Table 1](#). All efficacy and safety assessments during the FU phase will be assigned a day relative to this date. The FU study day in the FU treatment phase (ADY) is defined as:

$$\text{FU ADY} = \text{visit date} - \text{FU start date} + 1$$

for visits on or after FU Day 1.

### 2.1.3. Analysis Visits and Time Points

All visits for all assessments (safety, efficacy or PK) will be uniquely allocated within each phase to an analysis time point based on the target day according to [Table 2](#). All assignments will be made in chronological order. Once a visit is assigned to a visit window (Time interval in [Table 2](#)) it will no longer be used for a later time point except for the end of induction (EOI), which is the same visit as the consolidation baseline, the end of consolidation (EOC) and the end of study (EOS) visits, if applicable. If two or more visits fall within the same interval in the same phase, only one measurement will be selected for the analysis time point per phase in order to have only one evaluation per participant, except for the production of the spaghetti plots for which all measures will be displayed. The following rules will be applied:

1. The measurement closest to the target day in that phase will be used.
2. If the measurements fall equidistant from the target day, the last measurement in chronological order within the interval will be used per phase.

3. If there are two or more measurements on the same day, then the last measurement in chronological order will be used. If the time of the assessment is not available, the highest record/sequence number will be selected.

The listings will include all measurements, also those multiple assessments within the same visit window/phase.

End of induction (i.e., EOI), end of consolidation (i.e., EOC) and end of study (i.e., EOS) time points will be included in all analysis over time unless stated otherwise.

Because of the different scenarios for Cohort 1 vs Cohort 2 participants, a flag called Analysis Timepoint EOI (ATEOI) is created for each participant to identify the potentially different time point of end of induction phase. Similarly, an additional variable will be generated to identify the analysis timepoint for End of Consolidation (ATEOC).

Note: For the selection of the patient-reported outcome (PRO) measurements the above algorithm needs to be performed on the entire questionnaire (filled in at a specific date and time) and not on the individual questions /items (i.e., not mixing answers from different questionnaires).

**Table 2** provides the analysis time points, time intervals for each visit per analysis phase.

**Table 2: Analysis Time Points and Time Intervals by Analysis Phase**

**a) Screening and Induction Phases (Cohort 1 and 2)**

Analysis phase	Target day	Analysis time point (Week)			Analysis time point (label)	Time interval (Induction days)
		Cohort 1a a	Cohort 1b b	Cohort 2 c		
Screening	-∞	-1	-1	-1	Screening	<0
Induction	1	0	0	0	Baseline	Pre-dose: 1
	15	2	2	2	Week 2	[2,22]
	29	4	4	4	Week 4	[23,36]
	43	6	6	6	Week 6	[37,50]
	57	8	8	8	Week 8	[51, 71]
	85	12	12	12	Week 12	[72, 99]
	113	16	16	16	Week 16	[100, 127]
	141	20	20	20	Week 20	[128, 155]
	169	24	24	24	Week 24	[156, 183]
	197	28	28	28	Week 28	[184, 211]
	225	32	32	32	Week 32	[212, 239]
	253	36 a	36 b	36 c	Week 36	[240, 267]
	281	40 a	N/A	N/A	Week 40	[268, 295]
	309	44 a	N/A	N/A	Week 44	[296, 323]
	337	48 a	N/A	N/A	Week 48	[324,351]
	365	52 a	N/A	N/A	Week 52	[352, 379]
	393	56 a	N/A	N/A	Week 56	[380, 407]
	421	60 a	N/A	N/A	Week 60	[408, 435]
	last visit in induction phase	61 a, d	37 b, d	37 c, d	EOI d	

a If the participant was enrolled prior to the Protocol Amendment #5 was in effect (Cohort 1) and has already passed the Week 36 visit and/or has been randomized to the group without PegIFN- $\alpha$ 2a, then he/she will have PegIFN- $\alpha$ 2a added to their treatment regimen at the next scheduled visit. The EOI visit could occur between Week 36 and Week 60 (inclusive).

b If the participant was enrolled prior to the Protocol Amendment #5 was in effect (Cohort 1) and did not pass the Week 36 visit, he/she will have PegIFN- $\alpha$ 2a added to their treatment regimen at Week 36.

c If the participants was enrolled after the Protocol Amendment #6 (Cohort 2), he/she will have PegIFN- $\alpha$ 2a added to their treatment regimen at Week 36.

d End of induction phase (EOI) visit will be the last visit in Induction phase.

N/A=not applicable

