- b. All participants will have an end of induction phase visit at Week 36 (or later if they already passed the Week 36 visit at the time of Protocol Amendment 5) and enter the consolidation phase. Participants enrolled before Protocol Amendment 5 is in effect will switch to the new study design as soon as Protocol Amendment 5 is in effect. Participants who did not yet reach the Week 36 visit at that time will have PegIFN α2a added to their treatment regimen at Week 36 for 12 weeks. Participants who already passed the Week 36 visit and/or were randomized to the group without PegIFN α2a, will have PegIFN α2a added to their treatment regimen at the next scheduled visit.
- c. If necessary (eg, for operational reasons), the screening phase may be extended up to a maximum of 6 weeks in agreement with the sponsor.
- d. Day 1 samples are to be collected before the first dose of study intervention.
- e. The end of induction phase visit is equivalent to Day 1 of the consolidation phase (C D1). All assessments (with the exception of the sparse PK sample, which should be taken 2 8 hours after JNJ 3989 dosing) should be performed before administration/intake of JNJ 3989, PegIFN α2a, and NA. PegIFN α2a should be administered weekly, preferably in the evening by self injection. If desired, participants can also choose to have the administration of PegIFN α2a performed on site irrespective of the time of day.
- f. Participants who discontinue study intervention early will have an early WD visit and will enter follow up (see the Schedule of Activities Follow up Phase) unless they withdraw consent. Participants who withdraw consent will be offered an optional safety follow up visit to occur on the day of consent withdrawal. For the optional safety follow up visit, assessments are at the investigator's discretion and could be similar to the early WD visit.
- Both the Platform Master ICF and the ISA ICF must be signed before the first study related activity.

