### 2.2.2. Consolidation Baseline Timepoint

For the participants who receive PegIFN-  $\alpha$ 2a, the consolidation baseline assessment is defined as the date of first PegIFN-  $\alpha$ 2a intake. For the participants who did not receive PegIFN-  $\alpha$ 2a, the consolidation baseline will be defined as the date of any study agent intake after Max[Week 36 to 60 visit date] for Cohort 1 and the date of any study agent intake after Week 36 visit date for Cohort 2.

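### SAP Table 1 places a same-day pre-PegIFN Week 36 sample in consolidation, so Table 2 footnote d can pick Week 32 as end of induction, against SAP 2.1.3 and the protocol

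*SAP*

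**What the plan says.** **Phase dates.** For Cohort 1 participants who receive PegIFN without being randomized, the induction end date in SAP Table 1 opens "Min[Date of first PegIFN" and continues "2a intake-1 day, cut-off date": the earlier of the data cut-off and one day before first PegIFN. The Cohort 2 row for PegIFN recipients has the same rule. Consolidation starts on the first PegIFN date. For Cohort 2 participants without PegIFN, induction ends at the earliest of JNJ-3989 discontinuation, "early study withdrawal visit date, Week 36 visit date from induction phase", so a Week 36 visit can remain in induction.

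**End of induction (EOI).** Table 2 a), footnote d: "End of induction phase (EOI) visit will be the last visit in Induction phase". Section 2.1.3, when listing exceptions to the rule that a visit is used only once, names "the end of induction (EOI), which is the same visit as the consolidation baseline". The key to the SAP study schematics also equates the last induction visit with Day 1 of consolidation.

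**Consolidation baseline.** For PegIFN recipients, Section 2.2.2 gives a date and no pre-dose rule: "the consolidation baseline assessment is defined as the date of first PegIFN".

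**Protocol.** Section 1.3.1, footnote e, makes the end-of-induction visit and Consolidation Day 1 the same visit. All assessments except the sparse PK sample precede dosing. PegIFN is preferably self-injected in the evening. The note opening Section 1.3.2 repeats the equivalence.

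**Endpoint.** Both lists of objectives place the proportion with HBsAg below 10 IU/mL at end of induction, labelled Week 36. SAP 5.3.1.1.1 refers only to the end of induction, without naming EOI, consolidation baseline or a visit window.

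**The concern.** The natural sequence is a morning sample at the Week 36 visit followed by PegIFN on site or at home that evening. Table 1 works by calendar date, so that sample is a consolidation record even though it was drawn before PegIFN. A programmer who flags EOI as the last record dated in induction would then take the Week 32 visit. A programmer who follows Section 2.1.3 would take Week 36.

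The secondary endpoint could thus be read at different weeks for different participants, depending on whether PegIFN was injected on the visit date. EOI also feeds the cumulative-decline displays (SAP 5.3.2.1.5 and 5.4.2.1.2) and the HBQOL summaries (9.1.2). On the safety side, SAP 6.2.1 derives worst-case laboratory toxicity within each phase, so a pre-PegIFN Week 36 value would count under consolidation.

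**Working it through.** **1. Target days.** Target day = 7 × week + 1. Week 36: 7 × 36 + 1 = 253. Week 32: 7 × 32 + 1 = 225. Both match SAP Table 2 a). The gap is 253 − 225 = 28 days.

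**2. Apply Table 1 by date.** Induction end = first PegIFN day − 1. Consolidation day = visit day − first PegIFN day + 1. The protocol allows the Week 36 visit at Day 253 ± 3. The Week 32 visit is taken at Day 225.

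| Week 36 visit | First PegIFN | Induction ends | Last visit dated in induction |
|---|---|---|---|
| Day 250 | Day 250 | Day 249 | Day 225 (Week 32) |
| Day 253 | Day 253 | Day 252 | Day 225 (Week 32) |
| Day 256 | Day 256 | Day 255 | Day 225 (Week 32) |
| Day 250 | Day 251 | Day 250 | Day 250 (Week 36) |
| Day 253 | Day 254 | Day 253 | Day 253 (Week 36) |
| Day 253 | Day 255 | Day 254 | Day 253 (Week 36) |
| Day 256 | Day 257 | Day 256 | Day 256 (Week 36) |

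With same-day dosing the Week 36 sample is Consolidation Day 253 − 253 + 1 = 1. The induction Week 36 window, Days 240 to 267, then holds no induction record: the Week 32 visit falls at latest on Day 225 + 3 = 228.

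**3. Apply Section 2.1.3 to the same participant.** EOI is the consolidation-baseline visit. With same-day dosing that is the Day 253 visit, Week 36.

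**4. Compare.** Footnote d with Table 1 dates gives Day 225. Section 2.1.3 gives Day 253. The two rules agree only when PegIFN starts after the visit date, and even then Section 2.2.2 sets the consolidation baseline at the injection date, on which no visit need fall.

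**5. Who is affected.** The Week 32 result needs same-day dosing in a participant whose induction ends at Week 36 (the Cohort 1b and Cohort 2 columns of Table 2). It does not arise for later injectors or for participants who never receive PegIFN. For Cohort 1a participants past Week 36, the preceding visit is later than Week 32.

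**The case against.** The strongest reply is that the SAP already settles the matter. Section 2.1.3 addresses this dual-use visit directly and exempts it from the single-use rule so that one sample can serve twice. The SAP figure key and the protocol use the term last induction visit for the visit that is also Consolidation Day 1. Read in that sense, footnote d agrees with 2.1.3. Other markers point the same way: both documents label the endpoint Week 36, Table 2 b) codes the consolidation baseline as Week 36 for Cohorts 1b and 2, and footnote a puts EOI for Cohort 1a no earlier than Week 36.

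This stands as evidence of intent, and it defeats a stronger reading that a reader might infer: that the endpoint is in fact read at Week 32. The documents do not say that. Week 32 is what two of the rules yield when applied literally, for some participants only.

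It does not remove the conflict. Table 1 is the operative date derivation and has no exception for pre-dose samples on the first PegIFN date. Section 2.2.2 defines the consolidation baseline by a date alone, whereas study baseline (2.2.1) has an explicit pre-dose rule. The statement in 2.1.3 is an aside within the visit-reuse rule, and the endpoint definition refers to none of these places.

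**Conclusion.** The point holds as an internal inconsistency of minor weight. Table 1 and footnote d, applied by date, can select a visit 28 days earlier than the one that Section 2.1.3, the SAP figure key and the protocol intend. They also place pre-PegIFN Week 36 laboratory values in consolidation. The primary endpoint, read 24 weeks after treatment stops, is not affected.

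The Week 32 selection assumes that the first PegIFN dose falls on the visit date. The protocol's evening self-injection makes this plausible, but neither document says how often it happens.

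A reader might try to turn the 28 days into an HBsAg difference using the mean decline of 3.56 log10 IU/mL at Week 48 that the protocol's amendment history cites for currently untreated HBeAg-positive participants in REEF-1. That does not work. The figure comes from another study, the decline is described as biphasic with no Week 24 value given, and nothing shows how many participants here would lie near 10 IU/mL. The effect on the share below that threshold cannot be estimated from the documents.

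**What to change.** - **Table 1:** assign assessments taken on the date of the first PegIFN dose, and before that dose, to induction (Week 36/EOI), and reuse them as the consolidation baseline. If PegIFN starts after the visit date, use the last pre-PegIFN visit for both.
- **Table 2 a), footnote d:** define EOI as the last visit before the first PegIFN dose (Consolidation Day 1), or the last induction visit if PegIFN was never started.
- **Sections 5.3.1.1.1 and 2.2.2:** cross-reference that definition.

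The cost is a few lines of SAP wording and a check that the EOI flag and phase assignment are programmed to match. No new data or analyses are needed, and the change follows the intent already stated in Section 2.1.3 and the protocol.
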